3.2.3 Clinical Studies

A phase 3, multi-center, three-arm, randomized, open-label study was conducted in previously untreated patients with advanced renal cell carcinoma (clear cell and non-clear cell histologies). The objectives were to compare Overall Survival (OS), Progression-Free Survival (PFS), Objective Response Rate (ORR), and safety in patients receiving IFN- α to those receiving temsirolimus and temsirolimus plus IFN- α . Patients in this study had 3 or more of 6 pre-selected prognostic risk factors (less than one year from time of initial RCC diagnosis to randomization, Karnofsky performance status of 60 or 70, hemoglobin less than the lower limit of normal, corrected calcium of greater than 10 mg/dL, lactate dehydrogenase > 1.5 times the upper limit of normal, more than one metastatic organ site). Patients were stratified for prior nephrectomy status within three geographic regions and were randomly assigned (1:1:1) to receive IFN- α alone (n=207), temsirolimus alone (25 mg weekly; n=209), or the combination arm (n=210).

The ITT population for this interim analysis included 626 patients. Demographics were comparable between the three treatment arms with regard to age, gender, and race. The mean age of all groups was 59 years (range 23-86). Sixty-nine percent were male and 31% were female. The racial distribution for all groups was 91% White, 4% Black, 2% Asian, and 3% other. Sixty-seven percent of patients had a history of prior nephrectomy.

The median duration of treatment in the temsirolimus arm was 17 weeks (range 1-126 weeks). The median duration of treatment on the IFN arm was 8 weeks (range 1-124 weeks).

There was a statistically significant improvement in OS (time from randomization to death) in the temsirolimus 25 mg arm compared to IFN- α . The combination of temsirolimus 15 mg and IFN- α did not result in a significant increase in overall survival when compared with IFN- α alone.

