4.0 ELIGIBILITY CRITERIA

4.1 INCLUSION

1. Pathologic confirmation of metastatic or locally advanced RCC with a major clear cell component.
2. Measurable disease by RECIST criteria.
3. Age ≥ 18 years

4. ECOG performance status 0-2 or Karnofsky Performance Status \geq 60%
5. Meets criteria for poor-risk defined as 3 or more of the following: ECOG performance status 2, anemia (hemoglobin lower than reference range), elevated serum LDH $>1.5x$ upper limit of normal (ULN), hypercalcemia (corrected serum calcium level $>$ upper limit of normal), time from initial RCC diagnosis to registration on this trial $<$ 1 year, and $>$ 1 metastatic organ sites.
6. Adequate organ and marrow function within 14 days of registration as defined below:
 - Absolute neutrophil count $\geq 1,500/\mu\text{L}$
 - Platelets $\geq 100,000/\mu\text{L}$
 - Hgb ≥ 9.0 g/dL (transfusion allowed)
 - Renal: serum creatinine $\leq 1.5 \times$ ULN or calculated CrCl ≥ 40 cc/min and random urine protein:creatinine ratio (UPC) $<$ 1 or 24-hr urine protein $<$ 1g
 - Liver: total bilirubin ≤ 1.5 mg/dl; AST (SGOT) and ALT (SGPT) $\leq 2.5 \times$ ULN for subjects without evidence of liver metastases, $\leq 5 \times$ ULN for subjects with documented liver metastases
 - INR $\leq 1.2 \times$ ULN; PTT $\leq 1.5 \times$ ULN. Therapeutic anticoagulation with warfarin is allowed if target INR ≤ 3 on a stable dose of warfarin or on a stable dose of LMW heparin for $>$ 2 weeks (14 days) at time of randomization.
7. Female patients of childbearing potential (not postmenopausal for at least 12 months and not surgically sterile) must have a negative serum or urine pregnancy test within 14 days of study registration. Pregnancy test must be repeated if performed $>$ 14 days before starting study drug.

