5.0 TREATMENT PLAN

5.1 Study Summary

Patients with advanced poor-risk clear-cell RCC who have not had any prior systemic targeted therapy will be randomized fairly in a 1:1 ratio to receive pazopanib or temsirolimus as first-line therapy. Patients will be stratified upfront by nephrectomy status (yes/no) and prior cytokine/vaccine therapy (yes/no). At the time of disease progression, patients will be offered the option of crossover to receive the agent they did not receive in the first-line.

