13.0 STATISTICAL CONSIDERATIONS

This is a randomized, two-arm, parallel group, phase II trial enrolling advanced, poor-risk, clear-cell RCC. Patients will be fairly randomized to either temsirolimus (control arm) or pazopanib (experimental arm).

The maximum sample size to be accrued is 90 patients (45 in each treatment arm). The primary measure of efficacy and primary endpoint is progression free survival (PFS). PFS will be monitored on an interim basis and we will use stopping rules for futility to serve as guidelines for early termination. The stopping rules are ad-hoc in nature but are selected in a manner such that the overall type 1 error is controlled at a one-sided 10% with 80% power.

Descriptive and inferential statistics will be used to summarize treatment effects. The mean, standard deviation, median, 25% percentile, 75% percentile, minimum, and maximum will be reported for continuous variables. For discrete variables, descriptive analyses will be based on the distribution of discrete outcomes and will be reported as percentages and patient counts. Time to event endpoints will be descriptively summarized by Kaplan-Meier curves. Point and interval estimates of treatment effect will be based on maximum likelihood methods. For binomially distributed variables, we will report differences in proportions between treatment groups and the 95% confidence interval associated with those differences. We will estimate treatment effects for time to event variables via hazard ratios using Wald scores from Cox proportional hazard regression models. Unless stated otherwise, all statistical tests will be assessed using a two-sided $\alpha = 0.05$ alpha significance level and confidence intervals will be constructed using two-sided 95% and will be based on the normal approximation. Although multiple secondary endpoints will be evaluated we will make no adjustment for multiplicities associated with these multiple tests.

Estimation of Sample Size

The clinical hypothesis we are assessing in this trial is whether patients receiving the experimental therapy have a lower hazard of progression or death relative to patients receiving the control therapy. The statistical hypothesis is stated as:

$$H_0: \log(HR)=0$$

$$H_A: \log(HR)<0$$

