Where HR is the hazard ratio (experimental:control). For sample size calculation purposes we assume that the median PFS in the temsirolimus arm is 60% that of the pazopanib arm (3.8 months versus 6.1 months). The sample size estimate is based on a one-sided log-rank test with type one error equal to 0.10 and power of 0.80.

We will conduct an interim analysis for futility after 42 events have been observed. If the p-value used to assess futility at the interim analysis is greater than 0.4798 we will stop the trial early for futility.

Secondary Objectives

Overall survival: Overall survival is calculated from day of therapy initiation to the date of death. Patients who are lost to follow-up will be censored at date of last contact.

We will use the Kaplan-Meier estimator to estimate the OS for each group of patients (control, experimental), and the log-rank statistic will be used to test for treatment differences. We will also use the Cox proportional hazards regression model to estimate the hazard ratio (experimental:control) for OS with a 95% confidence interval.

We will also assess the response rate and report 95% confidence intervals.

Additional analyses:

Demographics

For each treatment group (control, experimental), summary statistics will be provided for age, weight, baseline disease status and prior treatments.

Toxicities

Toxicities and side effects that will be evaluated include, but are not limited to infections, renal toxicity, hepatic toxicity, and pulmonary toxicity. Methods of assessment will include monitoring blood counts, and performing laboratory tests as indicated by clinical signs and symptoms. Evidence of toxicities or adverse events will be recorded at all clinic visits. All observed toxicities and side effects will be graded (NCI CTC-AE v. 4.0) for all patients and the degree of association of each with pazopanib or temsirolimus assessed. The incidence and severity of toxicities will be compared between the two treatment arms with Fisher's exact test.

Stratification Factors

The Pocock-Simon Minimization Method will be used to randomize patients according to the following stratification factors:

- Prior nephrectomy status (yes or no)
- Prior cytokine/vaccine therapy (yes or no)

The randomization program based on this method will be developed in the Department of Biostatistics and Applied Mathematics, and the program will be available via an intranet web site of MD Anderson Cancer Center.

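### Section 13 names no covariates or strata for the PFS and OS analyses, although the number of poor-risk factors can be derived at baseline for every patient

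*Combined protocol and SAP*

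**What the plan says.** - **Test and power (section 13.0).** "The sample size estimate is based on a one-sided log-rank test with type one error equal to 0.10 and power of 0.80". The effect assumed is that "the median PFS in the temsirolimus arm is 60% that of the pazopanib arm (3.8 months versus 6.1 months"), and "The maximum sample size to be accrued is 90 patients (45 in each treatment arm").
- **Effect estimate (section 13.0).** "We will estimate treatment effects for time to event variables via hazard ratios using Wald scores from Cox proportional hazard regression models". Neither the log-rank test nor the Cox model is given covariates or strata, for PFS or for OS.
- **Interim (section 13.0).** "We will conduct an interim analysis for futility after 42 events have been observed". The trial stops if the p-value exceeds 0.4798. The test that yields this p-value is not named.
- **Allocation (sections 5.1 and 13.0).** Patients are "randomized fairly in a 1:1 ratio to receive pazopanib or temsirolimus as first-line therapy". Pocock-Simon minimisation uses two factors, prior nephrectomy and prior cytokine/vaccine therapy.
- **Risk factors.** Inclusion criterion 5 (section 4.1) reads "Meets criteria for poor-risk defined as 3 or more of the following" and lists six factors. Section 3.2.3 describes the earlier phase 3 temsirolimus trial: "Patients in this study had 3 or more of 6 pre-selected prognostic risk factors".
- **Baseline data (sections 5.3 and 5.3.1).** The work-up includes ECOG status, blood count, LDH, calcium, albumin, history and imaging, so all six factors can be derived before treatment.

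**The concern.** The trial holds baseline information on six factors for every patient, because eligibility depends on it. A near-identical list is described as prognostic in the trial from which the control-arm median is taken. Within the enrolled population the count still varies from 3 to 6, and neither the randomisation nor the analysis takes it into account.

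In a proportional hazards setting, leaving out a prognostic covariate pulls the estimated hazard ratio towards 1 and costs power, even when the arms are balanced. With 45 patients per arm, balance on an uncontrolled covariate is not assured either. Silence on covariates also leaves the primary model open. If an imbalance is noticed at analysis, any adjustment chosen then is post hoc.

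**Working it through.** **1. The plan's own figure.** Inputs from section 13.0: medians 3.8 and 6.1 months, one-sided alpha 0.10 (z = 1.2816), power 0.80 (z = 0.8416).
- HR = 3.8/6.1 = 0.623 (exponential PFS).
- Freedman: events = (1.2816 + 0.8416)² × [(1 + 0.623)/(1 − 0.623)]² = 4.508 × 18.53 = 83.5, so 84. Half of 84 is 42, the stated interim. The final event count is not stated; 84 is inferred.
- Schoenfeld: 4 × 4.508/(ln 0.623)² = 18.03/0.224 = 80.5, so 81.
- Power at 84 events with no interim: Φ(√84 × 0.473/2 − 1.2816) = Φ(0.887) = 0.81. With the futility rule at 42 of 84 events, power is 0.794 and type I error 0.094 (0.10 if the rule is not binding).

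The stated one-sided 10% and 80% power therefore reproduce.

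**2. Effect of adjusting for the count.** Three inputs are not in the documents and are assumed: the prognostic HR per extra factor, the distribution of the count, and accrual (uniform over 36 months, no dropout). In every setting the within-count treatment HR is 0.623 and the arm medians are 3.8 and 6.1 months. There were 10,000 simulated trials per setting, 45 per arm, analysed at the 84th event, one-sided 0.10, no interim. The Cox model used the count as a linear term.

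| HR per factor | Log-rank → adjusted Cox, counts 3/4/5/6 at 50/30/15/5% | Log-rank → adjusted Cox, counts at 70/22/7/1% |
|---|---|---|
| 1.0 | 80.5% → 80.3% | 79.8% → 79.7% |
| 1.25 | 78.1% → 79.6% | 79.7% → 79.5% |
| 1.5 | 75.7% → 80.2% | 78.3% → 80.0% |
| 2.0 | 70.0% → 79.5% | 74.8% → 80.2% |

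The Monte Carlo standard error is about 0.4 points. Type I error was 0.097 to 0.107 for both tests. The mean unadjusted HR drifted from about 0.62 (HR per factor 1.0) to 0.65-0.67 (HR per factor 2.0).

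**3. Count split as 3 v 4-6, stratified log-rank.** Assuming half the patients in each group (12,000 trials per setting), unadjusted v stratified power was 79.3% v 79.9% at a between-group HR of 1.5, 75.1% v 79.2% at 2.0, 72.4% v 79.5% at 2.5 and 69.1% v 79.6% at 3.0. With no prognostic effect it was 80.7% v 79.6%. Two further runs gave 80.4% v 79.0% and 79.8% v 78.2%, so the cost of needless stratification is about 1 to 1.5 points.

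**4. Chance imbalance.** With a 50/50 split and no balancing, the standard deviation of the between-arm difference in the proportion with 4-6 factors is √(2 × 0.25/45) = 0.105. In simulation about 35% of trials differed by 10 points or more. At a between-group HR of 2.0:
- when pazopanib drew the worse mix (about 17% of trials), power was 58% unadjusted and 77% stratified;
- when pazopanib drew the better mix and there was no true effect, the false-positive rate was 20% unadjusted and 10% stratified. At HR 1.5 it was 17% v 11%.

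**The case against.** The strongest reply is that the plan is not wrong. An unadjusted log-rank test is a legitimate choice for a 90-patient phase II trial at one-sided 10%. Its type I error holds on average, and its planned power reproduces. All of that stands.

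The prognostic premise is also weaker than it looks. A reader might infer that the protocol calls the number of factors prognostic. It does not. Section 3.2.3 applies the word to the individual factors in the earlier trial, and section 2.1 speaks only of prognostic models in general. The two lists also differ slightly: Karnofsky 60 or 70 against ECOG 2, and calcium above 10 mg/dL against above the upper limit of normal. Because entry already requires three factors, only the contrast between 3 and 6 matters. The documents give neither its size nor the expected distribution, so the gain is conditional.

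A reader might also infer that the count is a stronger predictor than the minimisation factors. No passage compares them. The one precedent described, the earlier phase 3 trial, stratified by nephrectomy within region, and no stratification by count is mentioned.

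Finally, section 13.0 is silent on covariates rather than committed to excluding them, and baseline disease status will be summarised by arm. An imbalance could therefore be seen, but the plan provides no way to correct for it. Silence on a primary model is itself a gap, and for the two minimisation factors that gap can be read from the text without assuming any effect size.

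**Conclusion.** The concern holds as a pre-specification gap and a possible missed gain in efficiency. It is not an error in the design. It would be wrong to conclude that the trial is underpowered as planned or that its type I error is inflated: neither follows from the documents, and step 1 of the working points the other way.

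Under the assumed count distributions and accrual, adjustment gains about 0 to 1.5 points of power at a prognostic HR of 1.25 per factor, 2 to 5 points at 1.5 and 5 to 10 points at 2.0. If the count is not prognostic, it costs about nothing with a Cox model and about 1.5 points with a stratified log-rank. The figures that condition on imbalance rest on an assumed even split of 3 v 4-6 and a between-group HR of 1.5 or 2.0. The effect of also adjusting for the minimisation factors was not simulated. The Cox figures use the count as a linear term, so a 3 v 4-6 indicator may recover somewhat less if risk rises steadily with each factor.

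The possible loss from adjusting is small and the possible gain is several points, so the change is worth making even though its benefit cannot be fixed in advance.

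**What to change.** In section 13.0, pre-specify that:

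1. the primary PFS treatment test and hazard ratio come from a Cox model adjusted for the baseline number of poor-risk factors (3 v 4-6), prior nephrectomy and prior cytokine/vaccine therapy, tested at one-sided 10%;
2. the same test supplies the p-value for the 42-event futility look;
3. the unadjusted log-rank test is a sensitivity analysis;
4. the OS analysis uses the same adjustment.

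A Cox model is preferable to full stratification. Three binary factors make 8 strata, which leaves about 11 patients per stratum (90/8) and about 5 events per stratum at the interim (42/8).

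The cost is a short amendment to section 13.0, including the interim paragraph. No new data are needed, because eligibility already requires the six factors. The count should be entered as a baseline variable for every patient, and the plan should say in advance what happens if a covariate level has too few events at the interim to be fitted.

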1.0 OBJECTIVES

Primary:

- To determine the progression-free survival (PFS) with pazopanib and temsirolimus in patients with advanced poor-risk clear-cell renal cell carcinoma (RCC).

Secondary:

- To determine the objective response rate (CR+PR) in patients with advanced poor-risk clear-cell RCC treated with pazopanib and temsirolimus.
- To determine the overall survival (OS) in patients with advanced poor-risk clear-cell RCC treated with pazopanib and temsirolimus.
- To determine the time to progression (TTP) in patients with advanced poor-risk clear-cell RCC treated with pazopanib and temsirolimus.
- To determine the duration of response in patients with advanced poor-risk clear-cell RCC treated with pazopanib and temsirolimus.
- To determine the safety associated with pazopanib and temsirolimus in patients with advanced poor-risk clear cell RCC.

Tertiary:

- To perform informative correlative studies in this disease state.
- To determine the safety and patient reported outcomes.

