2.3 Rationale

In the past few years, considerable progress has been made in the management of patients with metastatic renal cell carcinoma (RCC). There are now six (five in the first-line setting) FDA-approved treatments for metastatic RCC, however most patients experience disease progression within a year or less. The vast majority of metastatic RCC patients who were enrolled on phase 3 trials with anti-VEGF therapies, sorafenib, sunitinib, pazopanib and bevacizumab plus interferon alfa had good- or intermediate-risk disease. Temsirolimus is the standard of care for the treatment of patients with advanced poor-risk RCC, based on results from a phase 3 trial comparing single-agent temsirolimus versus single-agent interferon alfa versus the combination of temsirolimus and interferon alfa. The response rate of temsirolimus in this study was 8.4 %, and the median PFS and median OS were 3.8 months and 10.9 months, respectively. There is no data on the efficacy of multityrosine kinase inhibitors (TKI) in this disease state. Therefore, it is important to investigate agents with the oral convenience and tolerability of TKIs, such as pazopanib, in advanced poor-risk RCC.

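### The default normal-approximation interval for one arm's response rate falls short of 95% when response is low: at 45 patients and an assumed 8.4% it covers 89.8%, with a negative lower limit in 45% of trials

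*Combined protocol and SAP*

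**What the plan says.** Objective response is the first secondary objective in section 1.0: "To determine the objective response rate (CR+PR) in patients with advanced poor-risk clear-cell RCC". Section 13.0 then deals with intervals in three places.

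- The general rule, which applies wherever nothing else is specified: "confidence intervals will be constructed using two-sided 95% and will be based on the normal approximation".
- Binary variables compared between arms: "For binomially distributed variables, we will report differences in proportions between treatment groups and the 95% confidence interval associated with those differences".
- Response, under the secondary objectives: "We will also assess the response rate and report 95% confidence intervals".

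The last of these names no method, so the general rule governs it. No exact or score interval appears anywhere in the document. The only exact method named is Fisher's test, for comparing toxicities. The same section bases interval estimates of treatment effect on maximum likelihood and takes hazard ratios from Wald statistics, which points to the Wald interval as the intended normal approximation.

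The sample size is at most 45 patients per arm. No response rate is assumed for either arm. Section 2.3 reports the earlier phase 3 result for the control drug: "The response rate of temsirolimus in this study was 8.4" per cent.

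**The concern.** The Wald interval takes its standard error from the observed proportion. When the expected number of responders is small, that standard error is often far too small, and the interval is forced to be symmetric about an estimate close to zero. At 8.4% the expected count is 45 × 0.084 = 3.8 responders. Three faults then follow: coverage below 95%, lower limits below zero, and an interval of zero width when nobody responds.

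What is at stake is a secondary efficacy result. The arm's response rate would carry a 95% label that it does not meet, and the misses fall almost all on one side: the interval understates how high the true rate could be. If an impossible limit appeared and the method were then changed, the change would be made after seeing the data.

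**Working it through.** The plan gives no coverage or precision figure for this interval beyond the nominal 95%, so there is no stated figure to reproduce first.

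**Inputs.**
- n = 45 per arm (section 13.0).
- Two-sided 95%, z = 1.96 (section 13.0).
- True response rate p = 8.4%. This is an assumption, taken from section 2.3. The earlier trial enrolled patients of clear-cell and non-clear-cell histology who were all previously untreated (section 3.2.3). This trial requires a major clear-cell component and allows prior cytokines or vaccines (sections 4.1 and 4.2). A range of p is therefore shown as well.

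**Intervals, for x responders and p̂ = x/n.**
- Wald: p̂ ± z·√(p̂(1 − p̂)/n).
- Wilson: [p̂ + z²/(2n) ± z·√(p̂(1 − p̂)/n + z²/(4n²))] / (1 + z²/n).

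**Limits at low counts, n = 45.**

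| Responders | Wald | Wilson | P(x) at 8.4% |
|---|---|---|---|
| 0 | 0% to 0% | 0% to 7.9% | 0.0193 |
| 1 | −2.1% to 6.5% | 0.4% to 11.6% | 0.0796 |
| 2 | −1.6% to 10.5% | 1.2% to 14.8% | 0.1606 |
| 3 | −0.6% to 14.0% | 2.3% to 17.9% | 0.2111 |
| 4 | 0.6% to 17.2% | 3.5% to 20.7% | 0.2032 |

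**Coverage at p = 8.4%.** Coverage is the sum of the Binomial(45, 0.084) probabilities of those x whose interval contains 0.084.
- Wald contains it for x = 2 to 9: 0.1606 + 0.2111 + 0.2032 + 0.1528 + 0.0934 + 0.0477 + 0.0208 + 0.0078 = 0.897 (0.8975 unrounded).
- Wald upper limit below the truth, x = 0 or 1: 0.0193 + 0.0796 = 0.0989.
- Wald lower limit above the truth, x = 10 or more: 0.0036.
- Wald lower limit negative, x = 1, 2 or 3: 0.0796 + 0.1606 + 0.2111 = 0.4513.
- Wilson contains it for x = 1 to 7: 0.9485 (0.94848), that is 94.8%.
- Two million simulated trials gave 0.8974 for Wald coverage and 0.4512 for a negative lower limit.

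**Other true rates, n = 45.** Wald coverage moves unevenly with p:

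| True rate | 3% | 5% | 6% | 7% | 8% | 9% | 10% | 12% | 15% | 20% | 30% | 40% |
|---|---|---|---|---|---|---|---|---|---|---|---|---|
| Wald coverage | 74.4% | 89.9% | 93.3% | 82.9% | 87.6% | 91.6% | 93.6% | 91.3% | 90.9% | 95.1% | 93.9% | 93.0% |

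On a grid in steps of 0.05 percentage points:
- 5% to 10%: Wald 79.5% to 94.4%, mean about 89.5%. Wilson 93.5% to 97.9%, mean 95.8%.
- 10% to 20%: Wald mean 92.0%, minimum 85.9%.
- 20% to 40%: Wald mean about 93.5%, minimum 90.5%. Negative limits are rare here (1.3% of trials at 20%, 0.2% at 25%).

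**Smaller denominators.** Forty-five is a maximum, and section 14.2 bases the main response analysis on eligible patients. With 40 patients at 8.4%, Wald coverage is 85.5% and Wilson 95.3%.

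**Between-arm difference.** With 45 patients per arm and rates of 5%, 8.4% or 10% in one arm against 5% to 40% in the other, the Wald interval for the difference covers 93.6% to 95.1%. A finer grid, in half-point steps, gives 93.3% to 95.3%.

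**The case against.** Four points can be made in the plan's defence.

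- **The method is not fully specified.** A normal approximation need not mean Wald on the proportion scale; a Wilson interval also rests on one. This is fair as far as it goes. But Wald is the usual meaning, and the section's own maximum-likelihood and Wald wording supports it. If a score interval was intended, the text should say so.
- **8.4% is one point on a jagged curve, from a different population.** This stands as a limit on the exact figure. The general conclusion survives, because coverage stays below 95% at every rate on the 5% to 10% grid.
- **The consequence is small.** Response is secondary, no decision rule uses a single arm's interval, the between-arm difference is near nominal, and patient counts are to be reported, so a reader could recompute the interval. At 4 of 45 the two methods differ only by 0.6% to 17.2% against 3.5% to 20.7%. All true, and it limits the weight of the point. It does not make the reported 95% correct.
- **Wilson is not the only remedy.** The Clopper-Pearson interval covers 96.9% at 8.4% and would also serve. That is a choice between adequate methods, not a reason to keep the default.

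It would also be wrong to treat this as a problem of the temsirolimus arm alone. The plan gives no response rate for pazopanib in poor-risk disease, and the shortfall extends through 10% to 20%.

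**Conclusion.** The concern holds. Read as the Wald interval, the default does not deliver 95% for a single arm's response rate when that rate is low. With 45 patients and an assumed 8.4%, coverage is 89.8%, the lower limit is negative in 45.1% of trials, and a further 1.9% give an interval of zero width. Misses from too low an upper limit (9.9%) far outnumber those from too high a lower limit (0.4%). The shortfall is largest and most erratic below 10%, still material from 10% to 20%, and small on average above that. The conclusion rests on the Wald reading, on the response-rate interval being per arm (its natural meaning, since the difference is covered separately), and on a low true rate in at least one arm. It should be corrected, but it touches only a secondary result: the primary test, its error rates and the futility look do not depend on it.

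**What to change.** Add one sentence to section 13.0 as an exception to the default: *The objective response rate in each arm will be reported with a two-sided 95% Wilson score interval.* This covers both arms and cannot give a negative limit or a zero-width interval.

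For consistency only, the Newcombe interval could be named for the difference in response rates. The calculations show no need for it.

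The cost is one sentence and a standard software option. With 45 patients the Wilson interval sits higher and is somewhat wider at low counts: 11.2 against 8.6 percentage points with 1 responder, and 17.2 against 16.6 with 4. From 7 responders up it is slightly narrower, for example 26.1 against 27.1 with 14. Sample size, tests and error rates do not change.

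### Is the interim futility p-value of 0.4798 two-sided by default, so that power falls short of the stated 80%?

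*Combined protocol and SAP*

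**What the plan says.** All the relevant text is in section 13.0, Statistical Considerations, of the combined protocol and SAP.

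- **Interim rule** (Estimation of Sample Size): after 42 events, "If the p-value used to assess futility at the interim analysis is greater than 0.4798 we will stop the trial early for futility". Neither the sidedness of the p-value nor a final event count is given.
- **General default** (opening text): "Unless stated otherwise, all statistical tests will be assessed using a two-sided" 0.05 level.
- **Purpose of the stopping rules** (opening text): they are "selected in a manner such that the overall type 1 error is controlled at a one-sided 10% with 80% power". They are described as guidelines for early termination.
- **Hypothesis:** the question is whether "patients receiving the experimental therapy have a lower hazard of progression or death relative to patients receiving the control therapy", with alternative log(HR) < 0 for experimental versus control.
- **Sizing:** "The sample size estimate is based on a one-sided log-rank test with type one error equal to 0.10 and power of 0.80". The assumption is that the "median PFS in the temsirolimus arm is 60% that of the pazopanib arm (3.8 months versus 6.1 months"). The maximum enrolment is 90 patients, 45 per arm.

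**The concern.** The interim sentence stands alone, and a reader who applies the general default would take the p-value as two-sided. Routine log-rank output is often two-sided as well. The rule would then stop only for results near the null and would continue for results far from it in either direction. An observed hazard ratio against pazopanib would count as a reason to go on, which defeats the purpose of a futility look. It would also stop more often when pazopanib truly works, and the stated power would not be met.

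Two other details add to the doubt. No final event count is stated. The effect is described as 60% although 3.8/6.1 = 62.3%; an exact 60% would need a pazopanib median of 3.8/0.60 = 6.33 months. A hazard ratio of 0.60 would point to a smaller final analysis.

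**Working it through.** **Inputs from section 13.0.** Medians 3.8 and 6.1 months; one-sided alpha 0.10; power 0.80; interim at 42 events; threshold 0.4798. Allocation is 1:1 (section 5.1). **Assumptions:** exponential PFS, so HR = 3.8/6.1 = 0.623, and a final analysis at D events, with D not stated in the plan.

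**1. Events for a fixed design.** z(0.90) + z(0.80) = 1.2816 + 0.8416 = 2.1232, squared 4.508.

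- Schoenfeld, 4 × 4.508 / (ln HR)²: 80.5 events at HR 0.623; 69.1 at HR 0.60.
- Freedman, 4.508 × [(1 + HR)/(1 − HR)]²: 83.5 events at HR 0.623; 72.1 at HR 0.60.

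The planned 42 is half of 84. It fits the stated medians and not a ratio of exactly 0.60.

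**2. Where 0.4798 comes from.** Take one-sided alpha 0.10, power 0.80, one look at information fraction 0.5, O'Brien-Fleming-type beta spending and a binding bound. The spending function is an inference.

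- Beta spent at the look: 2 × [1 − Φ(z(0.90)/√0.5)] = 0.0699.
- Solving for the drift at the final analysis that gives 80% power: 2.1595.
- Interim bound: z = −1.4764 + 2.1595 × √0.5 = 0.0507, so one-sided p = 1 − Φ(0.0507) = 0.4798.
- Final critical value: z = 1.2453.
- Events: 4 × 2.1595² / (ln 0.623)² = 83.3, rounded up to 84, with half at 42.

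One design therefore returns the plan's threshold to four decimals together with its interim event count. The threshold is evidently a one-sided p.

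**3. Operating characteristics of the two readings.** The log-rank Z at 42 and D events is bivariate normal with correlation √(42/D) and mean −ln(HR) × √events / 2. The final test is at z = 1.2816.

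| | One-sided p | Two-sided p |
|---|---|---|
| Stop if | Z < 0.051 | absolute Z < 0.707 |
| Observed HR that stops | above about 0.984 | about 0.80 to 1.24 |
| Stops at true HR 0.623 | 6.9% | 19.2% |
| Power, D = 80 | 78.3% | 71.4% |
| Power, D = 84 | 79.4% | 72.0% |
| Power, D = 90 | 81.0% | 73.0% |
| Type I error, D = 84 | 9.4% | 7.6% |
| Continues at true HR 1.5 | 8.6% | 75.0% |

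The HR limits are exp(−2 × 0.0507/√42) = 0.984 and exp(±2 × 0.7066/√42) = 0.804 and 1.244. A simulation of 20,000 log-rank trials (90 patients; uniform 30-month accrual and no dropout assumed) gave 78.3% and 71.0% power at D = 84.

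**4. Binding or not.** At D = 84 with the one-sided rule, a final critical value of 1.2453 (one-sided p below 0.1065) gives type I error 10.0% and power 80.2%. Keeping 1.2816 gives 79.4%. The difference is under one point.

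**The case for a change.** The best case for a change is that the interim sentence cannot be carried out from its own words. It names no direction, a conflicting default sits in the same section, and the two readings are very different trials. No final count possible with 90 patients rescues the two-sided one, whose power is still only 73.0% at 90 events. If the 60% figure were used to set the final count at 70 to 73 events, power at the stated medians would be about 75% to 76% even with the one-sided rule. The repair would be a few words and would cost no patients.

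The calculations stand, and so does the observation that the sentence omits the word one-sided and that the final count is not given. The inference to a defect does not. The default yields wherever the section says otherwise, and it does so for PFS three times: in the alternative hypothesis, in the test used for sizing, and in the error rate that the stopping rules were chosen to meet. A threshold near 0.48 is also plainly not a test at the default 0.05 level. The 70 to 73 event scenario conflicts with the medians printed in the same sentence and with an interim at 42. Because the rules are guidelines, even a misread p-value would not oblige anyone to continue a trial leaning against pazopanib.

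**Conclusion.** The concern does not hold. On the reading that section 13.0 supports, the rule stops when the observed hazard ratio is above about 0.98, and the stated 10% error and 80% power are met to within two points. The 72% power, the 19.2% chance of stopping an effective drug and the 75% continuation at a true hazard ratio of 1.5 describe a misreading.

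What remains is small. The sidedness is left to context that settles it. Any final count from 80 to 90 events gives 78% to 81% power. The 60% is a loose rounding of 62.3% beside the actual medians. Binding status moves power by less than one point. A one-line clarification would be harmless, but a statistician following the section as a whole reaches the same result without it.

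This rests on exponential PFS with HR 0.623, the usual normal approximation for the log-rank test, and a final count near 84, which is inferred and not stated. The match in step 2 also depends on an inferred spending function. The textual argument for a one-sided p-value does not depend on it.
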